#### **4.6.2 Patient Discontinuation from Study**

Patients will return to the clinic for a study discontinuation visit at treatment discontinuation.

Patients have the right to voluntarily withdraw from the study at any time for any reason. In addition, the investigator has the right to withdraw a patient from the study at any time. Reasons for withdrawal from the study may include, but are not limited to, the following:

- Patient withdrawal of consent
- Study termination or site closure
- Patient non-compliance, defined as failure to comply with protocol requirements as determined by the investigator or Sponsor

Every effort should be made to obtain information on patients who withdraw from the study. The primary reason for withdrawal from the study should be documented on the appropriate eCRF. If a patient requests to be withdrawn from the study, this request must be documented in the source documents and signed by the investigator. Patients who withdraw from the study will not be replaced.

#### **4.6.3 Study Discontinuation**

The Sponsor has the right to terminate this study at any time. Reasons for terminating the study may include, but are not limited to, the following:

- The incidence or severity of adverse events in this or other studies indicates a potential health hazard to patients
- Patient enrollment is unsatisfactory

The Sponsor will notify the investigator if the Sponsor decides to discontinue the study.

#### **4.6.4 Site Discontinuation**

The Sponsor has the right to close a site at any time. Reasons for closing a site may include, but are not limited to, the following:

- Excessively slow recruitment
- Poor protocol adherence
- Inaccurate or incomplete data recording
- Non-compliance with the International Council for Harmonisation (ICH) guideline for Good Clinical Practice
- No study activity (i.e., all patients have completed the study and all obligations have been fulfilled)

### **5. ASSESSMENT OF SAFETY**

#### **5.1 SAFETY PLAN**

DHES0815A is not approved, and clinical development is ongoing. This is the first study in which DHES0815A will be administered to humans. The safety plan for patients in this study is based on nonclinical experience with DHES0815A, clinical experience with HER2-targeting molecules (i.e., trastuzumab, pertuzumab, and trastuzumab emtansine), and published clinical data of rovalpituzumab tesirine (DLL3-targeting ADC linked to a

PBD dimer; Rudin et al. 2017) and SJG-136 (PBD dimer; Hochhauser et al. 2009). The anticipated important potential safety risks for DHES0815A are outlined below. Please refer to the DHES0815A Investigator's Brochure for a complete summary of safety information.

Several measures will be taken to ensure the safety of patients participating in this study. Eligibility criteria have been designed to exclude patients at higher risk for toxicities. Patients will undergo safety monitoring during the study, including assessment of the nature, frequency, and severity of adverse events. In addition, guidelines for managing adverse events, including criteria for dosage modification and treatment interruption or discontinuation, are provided below.

### **5.1.1 Potential Risks Associated with DHES0815A**

#### **5.1.1.1 Left Ventricular Dysfunction**

Patients treated with DHES0815A may be at risk of developing left ventricular dysfunction. Significant cardiac events, including LVEF of <40%, have been observed with HER2-targeting molecules (i.e., trastuzumab, pertuzumab, and trastuzumab emtansine).

Patients must meet specified LVEF requirements to be included in this study (see Section 4.1.2).

Left ventricular function will be monitored by measurement of ejection fraction using ECHO (or MUGA) scans as described in Section 4.5.8 and the schedule of activities (see [Appendix 1](#)).

Guidelines for management of patients who develop left ventricular dysfunction are provided in [Table 3](#).

#### **5.1.1.2 Dermatologic Toxicity**

Skin disorders, including hyperpigmentation, erythema, and rash may occur in patients treated with DHES0815A. In nonclinical studies, hyperpigmentation has been observed in cynomolgus monkeys and did not reverse during the recovery period. HER2-targeting molecules can cause skin disorders, including erythema, rash, and pruritus. Skin disorders have also been observed with rovalpituzumab tesirine, including Grade  $\geq 3$  events of rash, erythema, and photosensitivity (Rudin et al 2017).

Patients should be monitored closely for skin toxicity. Patients are advised to prevent exposure to UV light and apply sunscreen to exposed areas of the skin when outside in the sun. If skin toxicity occurs, patients should be evaluated by a dermatologist, and a proper dermatologic diagnosis should be established and recorded on the eCRF. For Grade  $\geq 2$  dermatologic events, photographs of the affected area should be obtained if possible and submitted to the sponsor to document the type and course of the skin toxicity. The photographs will be taken in such a manner as not to create any risk of

identifying the patient; photographs will be thoroughly de-identified at the sites prior to providing them to the Sponsor.

#### **5.1.1.3 Hematological Toxicity**

In nonclinical studies, mild decreases in lymphocytes, eosinophils, and reticulocytes have been observed in cynomolgus monkeys. In addition, minimal lymphoid depletion was noted in spleen and lymph nodes. Thrombocytopenia has been reported in patients in clinical trials of trastuzumab emtansine and cases of severe bleeding events, some with a fatal outcome, have been observed (Kadcyla® U.S. Package Insert). Declines in other hematopoietic lineages were less frequent with the use of trastuzumab emtansine than that observed for platelets. Thrombocytopenia also occurred in 12% of patients treated with rovalpituzumab tesirine (including two Grade 4 and one fatal event; Rudin et al. 2017).

Hematologic laboratory parameters will be monitored as described in Section 4.5.6 and the schedule of activities (see [Appendix 1](#)). Guidelines for management of DHES0815A in patients who develop hematologic toxicity are provided in [Table 3](#).

#### **5.1.1.4 Nephrotoxicity**

No renal findings or changes in urinalysis were observed in GLP toxicology studies with DHES0815A in cynomolgus monkeys. However, tubular degeneration had been seen in nonclinical studies at higher doses of DHES0815A than were tested in the GLP toxicology studies.

Patients with a baseline serum creatinine level higher than  $1.5 \times \text{ULN}$  or creatinine clearance  $< 65 \text{ mL/min}$  will be excluded from this study. To address potential renal toxicity, BUN and creatinine will be measured frequently and urinalysis will be done at each cycle.

#### **5.1.1.5 Hepatic Toxicity**

No pathological liver findings and no changes in liver function tests were observed in GLP toxicology studies in cynomolgus monkeys. Hepatic toxicity (including liver failure and death) and nodular regenerative hyperplasia of the liver are identified risks for trastuzumab emtansine and elevated transaminases (Grades 2–4) were observed with both SJG-136 (Hochhauser et al. 2009) and rovalpituzumab tesirine (Rudin et al. 2017).

Patients must meet specified hepatic laboratory test requirements to be included in this study (see Section 4.1.2). Hepatic laboratory parameters will be monitored as described in Section 3.1.1.1 and the schedule of activities (see [Appendix 1](#)).

#### **5.1.1.6 Ocular Toxicity**

In GLP toxicology studies in cynomolgus monkeys, corneal pigmentation was observed after administration of DHES0815A. Ocular toxicity is therefore a potential risk for patients treated with DHES0815A and may present with impaired vision.

Ophthalmic examinations will include assessment of BCVA and an anterior segment slitlamp examination with fluorescein. Ophthalmic examinations must be conducted during the screening period, during the last week (Days 15–21) of even-numbered cycles until Cycle 6 (i.e., at Cycles 2, 4, and 6) and every four cycles thereafter (i.e., at Cycles 10, 14, 18, etc.), and at the study discontinuation visit (unless the most recent ophthalmic examination has occurred within the past 4 weeks). Patients who experience ocular symptoms, including but not limited, to eye pain, dry eyes, blurred vision, or a decline in visual acuity, will be required to undergo an ophthalmic examination at an unscheduled visit as soon as practical. Such visits should include the same assessments as those described above, along with any additional assessments deemed clinically indicated per standard of care.

If no study drug–related ophthalmic adverse events Grade  $\geq 2$  are reported during dose escalation, ophthalmic examinations may not be required for patients enrolled in the expansion cohort.

#### **5.1.1.7 Pulmonary Toxicity**

In GLP toxicology studies in cynomolgus monkeys, an increase in alveolar macrophages was observed after the administration of DHES0815A. Mild alveolar degeneration and fibroplasia was observed in nonclinical studies when cynomolgus monkeys received DHES0815A at dose levels higher than those given in the GLP toxicology studies. Cases of interstitial lung disease, including pneumonitis, some leading to acute respiratory distress syndrome or death, have been reported in patients receiving HER2-targeting drugs (i.e., trastuzumab, pertuzumab, trastuzumab emtansine). Signs and symptoms may include dyspnea, cough, fatigue, and pulmonary infiltrates. Patients with dyspnea at rest due to complications of advanced malignancy and comorbidities may be at risk of pulmonary events. Therefore, patients with clinically significant pulmonary symptoms or disease will be excluded from this study (see Section 4.1.2). Patients who develop new respiratory symptoms or imaging findings suggestive of pulmonary toxicity should be evaluated by a pulmonologist.

#### **5.1.1.8 Vascular Leak Syndrome**

GLP studies in cynomolgus monkeys receiving DHES0815A did not reveal indications for vascular leak, edema, or serosal effusion. In clinical trials with SJG-136 (Hochhauser et al. 2009) and rovalpituzumab tesirine (Rudin et al. 2017), vascular leak syndrome, serosal effusions, and edema were observed.

Patients treated with DHES0815A will be closely monitored for clinical signs and symptoms indicating vascular leak. As part of scheduled tumor assessment, CT or MRI imaging of chest and abdomen will be performed that may also be assessed for evidence of internal effusions.

### **5.1.1.9 Gastrointestinal Toxicity**

Gastrointestinal toxicity (watery diarrhea, mucosal atrophy in small and large intestine and stomach) was observed in nonclinical studies when cynomolgus monkeys received DHES0815A at dose levels higher than those given in the GLP toxicity study.

Patients will be closely monitored for clinical signs of gastrointestinal toxicity, and supportive treatment will be initiated at the investigator's discretion.

### **5.1.1.10 Infusion-Related Reactions, Hypersensitivity, Anaphylaxis**

Some MAbs may be associated with the development of allergic or anaphylactic reactions to either the active protein or excipients. True allergic/anaphylactic reactions are rare with the first dose of a product, because they require prior sensitization.

Patients with true allergic/anaphylactic reactions should not receive further doses of the product.

MAbs may also be associated with reactions that are clinically indistinguishable from true allergic/anaphylactic reactions but that are mediated through direct release of cytokines or other pro-inflammatory mediators. Such reactions are often termed IRRs. IRRs typically occur with the first infusion of a MAb product and are generally less frequent and/or less severe with subsequent infusions. They can often be managed by slowing the infusion rate and/or pretreatment with various medications.

Despite the different pathophysiology of IRRs (reactions involving cytokine release) and hypersensitivity (allergic) reactions, the clinical manifestations are the same and include flushing, chills, pyrexia, dyspnea, hypotension, wheezing, bronchospasm, and tachycardia. Allergic/anaphylactic reactions and IRRs typically begin during or within several hours after completing the infusion. The onset of symptoms may be rapid, and some reactions may be life threatening.

Patients with a history of allergic/anaphylactic reactions to MAbs, including trastuzumab, pertuzumab, or trastuzumab emtansine, will be excluded from this study (see Section 4.1.2).

Administration of DHES0815A will be performed in a setting with access to emergency facilities and staff who are trained to monitor and respond to medical emergencies.

Patients should be closely monitored for IRRs during and after each infusion of DHES0815A, as described in Section 4.3.2.

Guidelines for management of patients who experience IRRs or hypersensitivity reactions are provided in [Table 3](#). Please see [Appendix 6](#) for guidance on anaphylaxis precautions.

### **5.1.1.11 Immunogenicity**

As with any recombinant antibody, DHES0815A may elicit an immune response and patients may develop antibodies against DHES0815A. ADA response and potential

correlation of response to relevant clinical safety endpoints will therefore be assessed for all treated patients. Validated screening and confirmatory assays with appropriate sensitivity and therapeutic tolerance will be employed to detect ADAs at multiple timepoints before, during, and after treatment with DHES0815A. Serum samples will be collected from all patients prior to their first dose of DHES0815A and at several additional timepoints (see [Appendix 2](#)).

### **5.1.2        Management of Patients Who Experience Adverse Events**

#### **5.1.2.1      Dose and Schedule Modifications**

The dose of DHES0815A can be reduced by one dose level up to two times for management of drug-related toxicities. If further dose reduction is indicated after two dose reductions, the patient must discontinue DHES0815A. Dose increases after prior dose reduction for drug-related toxicities will not be permitted.

DHES0815A treatment may be temporarily suspended in patients who experience toxicity considered to be related to study drug. Dose delays for >14 days because of toxicity have to be discussed with and approved by the Medical Monitor; otherwise, the patient should be discontinued from DHES0815A. DHES0815A treatment may be suspended for reasons other than toxicity (e.g., surgical procedures) with Medical Monitor approval. The investigator and the Medical Monitor will determine the acceptable length of treatment interruption.

#### **5.1.2.2      Management Guidelines for Patients Who Experience Adverse Events**

Guidelines for managing DHES0815A-related toxicities other than the ones specified in [Table 3](#) are as follows:

- For Grade  $\geq 3$  adverse events: DHES0815A treatment should be withheld for Grade  $\geq 3$  DHES0815A-related toxicities that have not recovered to Grade  $\leq 1$  or baseline prior to planned dosing. The next scheduled dose may be delayed by up to 14 days. Longer dose interruptions are only allowed upon discussion with the Medical Monitor. If improvement to Grade  $\leq 1$  or baseline does not occur within 14 days (or a longer interval approved by the Medical Monitor), DHES0815A treatment should be discontinued. If the DHES0815A-related toxicity improves to Grade  $\leq 1$  or baseline, DHES0815A may be restarted at a reduced dose.

The DHES0815A dose in subsequent cycles should be reduced to either the next lowest dose level tested in dose escalation for patients in the dose escalation cohort, or by approximately 25%–50% (upon discussion with the Medical Monitor) for patients in the expansion cohort. No more than two dose reductions are permitted on study.

- For Grade 2 adverse events: DHES0815A treatment should be withheld for Grade 2 DHES0815A-related toxicities that have not recovered to Grade 1 or baseline prior to planned dosing. The next scheduled dose may be delayed by 14 days. Longer dose interruptions may be allowed upon discussion with the Medical Monitor. If improvement to Grade  $\leq 1$  or baseline does not occur within

14 days (or a longer interval approved by the Medical Monitor), DHES0815A treatment should be discontinued. If the DHES0815A-related toxicity improves to Grade  $\leq 1$  or baseline, DHES0815A may be restarted at the current dose.

### **5.1.2.3 Management Guidelines for Patients Who Experience Specific Adverse Events**

Guidelines for management of specific adverse events (hematologic toxicity and IRRs/hypersensitivity) are outlined in [Table 3](#). Additional guidelines are provided in [Figure 2](#) (left ventricular dysfunction) and below for increases in QT interval and ocular toxicities.

[figure not shown]
**Table 3 Guidelines for Management of Patients Who Experience Specific Adverse Events**

Event	Action to Be Taken
Hematologic toxicity as manifested in any one of the below laboratory abnormalities: 

• Absolute neutrophils <math>< 1500/\text{mm}^3</math>

• Hemoglobin <math>< 8 \text{ g/dL}</math>

• Platelets <math>< 100,000/\text{mm}^3</math>

	

Withhold all study treatment up to 14 days; longer dose interruption may be allowed upon discussion with the Medical Monitor.

Give supportive treatment as clinically indicated per local practice.

Resume DHES0815A treatment if ANC <math>\geq 1500/\text{mm}^3</math>, platelets <math>\geq 100,000/\text{mm}^3</math>, and hemoglobin <math>\geq 8 \text{ g/dL}</math>.

If hematologic toxicity leading to dose hold recurs in consecutive cycles, resume DHES0815A treatment at a reduced dose if ANC <math>\geq 1500/\text{mm}^3</math>, platelets <math>\geq 100,000/\text{mm}^3</math>, and hemoglobin <math>\geq 8 \text{ g/dL}</math>.

If hematologic toxicity leading to dose hold occurs in two consecutive cycles at the reduced dose, discontinue DHES0815A.

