#### **3.1.1.1 Definition of Dose-Limiting Toxicity**

For dose-escalation purposes, any one of the following events will be considered a DLT if it occurs during the DLT assessment window, unless clearly attributed to another identified etiology by the investigator (e.g., cancer progression):

- $\geq 15\%$  decrease from baseline in LVEF or  $\geq 10\%$  decrease to less than a 50% LVEF
- Grade  $\geq 3$  non-hematologic toxicity with the following exceptions:
  - Grade 3 nausea, vomiting, or diarrhea that resolves to Grade  $\leq 1$  with standard-of-care therapy in  $\leq 7$  days
  - Grade 3 fatigue that resolves to Grade  $\leq 2$  in  $\leq 7$  days
  - Grade 3 elevation of serum hepatic transaminase (ALT or AST) without an increase in direct bilirubin  $> 2 \times$  upper limit of normal (ULN) or clinical jaundice and lasting  $< 7$  days
  - Grade 3 laboratory abnormalities that are asymptomatic and considered by the investigator not to be clinically significant
- Grade  $\geq 4$  neutropenia (ANC  $< 500$  cells/ $\mu$ L) lasting  $> 7$  days
- Grade  $\geq 3$  febrile neutropenia
- Grade  $\geq 4$  anemia

- Grade  $\geq 4$  thrombocytopenia
- Grade 3 thrombocytopenia associated with clinically significant bleeding
- Any increase in hepatic transaminase (ALT or AST)  $> 3 \times$  baseline in combination with either an increase in direct bilirubin  $> 2 \times$  ULN or clinical jaundice, in the absence of cholestasis or other contributory factors (e.g., worsening of metastatic disease, concomitant exposure to known hepatotoxic agent, or documented infectious etiology).

This is suggestive of potential drug-induced liver injury (according to Hy's Law) and will be considered a DLT.

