### **3.1.1.4      Continuation of DHES0815A (Cycles $\geq 2$ )**

Patients without a DLT during the DLT assessment window will be eligible to receive additional infusions of DHES0815A at the same dose level at which they were enrolled or at an increased dose as detailed in Section [3.1.1.3](#) (the day of infusion being Day 1 of each cycle), provided that they meet the following criteria for acceptable toxicity and ongoing clinical benefit:

- Acceptable toxicity: All adverse events experienced with prior infusions that were not attributed to constitutional symptoms of the patient's cancer or intercurrent illness must have decreased to Grade 1 or baseline grade on or before the day of the next infusion.

Exceptions on the basis of ongoing clinical benefit may be allowed after a careful assessment and discussion of benefit versus risk with the patient by the investigator and approval from the Medical Monitor. In addition, delay of therapy because of toxicities not attributed to study drug may not require discontinuation

from the study but must be approved by the Medical Monitor. Dose modifications are described in Section 5.1.2.1.

- Ongoing clinical benefit: Patients must demonstrate improvement/stabilization in tumor burden, according to the RECIST v1.1 ([Appendix 3](#)) or demonstrate clinical signs or symptoms of benefit, as judged by the investigator, independent of RECIST.

All tumors assessed at screening must be documented and re-assessed at each subsequent tumor evaluation (see [Appendix 1](#) for tumor assessment schedule). For each patient, the same imaging modality should be used throughout the study.

*For patients in Cohorts 1–5, please also refer to Section 3.1.*

Women of childbearing potential will need to undergo a urine pregnancy test prior to each DHES0815A cycle (patients whose breast tumor produces human chorionic gonadotropin [hCG] and were confirmed not to be pregnant prior to enrollment should be monitored with serum pregnancy tests rather than urine pregnancy tests prior to each cycle of study treatment). If a urine pregnancy test result is positive, patient dosing will be postponed until the result is confirmed by a serum pregnancy test. Patients who are pregnant must permanently discontinue study treatment.

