DHES0815A administration will be discontinued in patients who experience a DLT during the DLT assessment window (Days 1–21 of the first cycle) if this toxicity does not return to baseline grade within 14 days. Patients who experience a DLT during the first cycle (Days 1–21) and whose toxicity returns to baseline within 14 days may be restarted at a dose level tolerated by the prior cohort following discussion with the Medical Monitor. A treatment delay beyond 14 days may be acceptable upon discussion with the Medical Monitor (see Section 5.1.2.1).

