### **3.1.2 Expansion Stage**

After dose escalation has been completed, up to approximately 25 patients may be enrolled in the expansion stage. Patients may be treated at or below the MTD or MAD to obtain additional safety, tolerability, and PK data, as well as preliminary evidence of anti-tumor activity.

If the frequency of Grade 3 or 4 toxicities or other unacceptable toxicities at the initial expansion-stage dose level suggest that the MTD has been exceeded, accrual at that dose level of DHES0815A will be halted. Consideration will then be given to enrolling patients in an expansion cohort at a lower dose level.

Patients in the dose-expansion cohort will be eligible to receive DHES0815A treatment after Cycle 1 provided that they meet the same criteria for acceptable toxicity and ongoing clinical benefit as outlined for the dose-escalation cohorts in Section 3.1.1.4.

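### After a first isolated DLT-level cytopenia in Cycle 2 or later of escalation, or in any cycle of expansion, Table 3 sets no reduced dose as the default for re-treatment

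*Combined protocol and SAP*

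**What the plan says.** **Table 3 (Section 5.1.2.3).** The hematologic row is triggered by an ANC below 1500, hemoglobin below 8 g/dL or platelets below 100,000, whatever the grade. A first event leads to a hold of up to 14 days, extendable with the Medical Monitor, and then resumption once counts recover. The row does not state the dose at that first resumption. A lower dose appears only at the next step: "If hematologic toxicity leading to dose hold recurs in consecutive cycles, resume DHES0815A treatment at a reduced dose", again subject to count recovery.

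**Section 5.1.2.2** limits its own scope: "Guidelines for managing DHES0815A-related toxicities other than the ones specified in" Table 3. For related Grade 3 or higher toxicity within that scope it states: "The DHES0815A dose in subsequent cycles should be reduced to either the next lowest dose level tested in dose escalation" for escalation patients, or by roughly 25% to 50% for expansion patients.

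**Section 5.1.2.1** is permissive: "The dose of DHES0815A can be reduced by one dose level up to two times for management of drug-related toxicities".

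**Section 3.1.1.4** has a restart rule for DLTs in Days 1–21 of Cycle 1. It applies to patients "whose toxicity returns to baseline within 14 days may be restarted at a dose level tolerated by the prior cohort". Of the others it says: "Patients without a DLT during the DLT assessment window will be eligible to receive additional infusions of DHES0815A at the same dose level", or at an increased one where intrapatient escalation applies, subject to toxicity and benefit criteria.

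**Section 3.1.2** lets expansion patients continue after Cycle 1 "provided that they meet the same criteria for acceptable toxicity and ongoing clinical benefit as outlined for the dose-escalation cohorts".

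**Section 3.1.1.1** defines the events at issue and ties them to the escalation window: "For dose-escalation purposes, any one of the following events will be considered a DLT if it occurs during the DLT assessment window".

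**The concern.** The protocol regards a Grade 4 thrombocytopenia as serious enough to be dose-limiting, and in escalation Cycle 1 it attaches a lower restart dose to that event. One cycle later, or in expansion, the identical event carries no default reduction, and no reason for the difference is given. In expansion Cycle 1 the contrast is sharper: the event counts toward pausing accrual under Section 6.1.2, yet no rule asks for a lower dose in the patient who had it.

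At stake is the individual patient's next dose. Section 5.1.1.3 cites thrombocytopenia with severe and sometimes fatal bleeding for trastuzumab emtansine, and Grade 4 and fatal thrombocytopenia for a PBD-dimer conjugate. Without a default, sites may re-treat the same event at different doses. That also adds avoidable variation to dose intensity and number of cycles, which are endpoints under the primary objective in Table 1.

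**Working it through.** The plan has no figure to reproduce here. The check traces which rule sets the next dose after a first isolated laboratory cytopenia that meets a Section 3.1.1.1 criterion: Grade 4 thrombocytopenia, Grade 4 anemia, or Grade 4 neutropenia lasting more than 7 days.

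**Step 1. Rules by setting**

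| Setting | Rule that sets the next dose | Default next dose after recovery |
|---|---|---|
| Escalation, Cycle 1 | 3.1.1.4 | A level the prior cohort tolerated |
| Escalation, Cycle 2 or later | Table 3 | None; full dose allowed |
| Expansion, Cycle 1 | Table 3 | None; full dose allowed |
| Expansion, Cycle 2 or later | Table 3 | None; full dose allowed |
| Comparator: related Grade 3 or higher toxicity governed by 5.1.2.2 | 5.1.2.2 | Next lowest tested level (escalation) or about 25%–50% lower (expansion) |

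**Step 2. Whether another rule fills the three open rows**

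- Section 5.1.2.2 does not, because it excludes what Table 3 specifies, and hematologic toxicity is specified there.
- Section 5.1.2.1 allows a reduction but does not ask for one.
- The restart rule in Section 3.1.1.4 is confined to the first 21 days, sits under the escalation stage and is expressed through a prior cohort.
- Section 3.1.2 brings into expansion only the acceptable-toxicity and benefit criteria. The toxicity criterion (recovery to Grade 1 or baseline) governs when the next infusion may be given, not at what dose.
- Sections 3.1.2 and 6.1.2 otherwise act on cohort accrual.

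**Step 3. Size of the dose difference**

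- Expansion: a 25%–50% reduction leaves 75%–50% of the dose. Full dose relative to reduced dose: 1/0.75 = 1.33 and 1/0.50 = 2.0.
- Escalation: Section 3.1 caps Cohorts 1–5 at 2.4 mg/kg, and the tested levels at or below the cap are 0.6, 1.2 and 2.4 mg/kg. One step down is a halving: 2.4/1.2 = 2.0 and 1.2/0.6 = 2.0. At 0.6 mg/kg the documents show no lower tested level.

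**Step 4. Events needed before a reduction is called for**

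- Section 5.1.2.2: 1.
- Table 3: at least 2, each causing a hold, in consecutive cycles.
- Holds in alternate cycles, for example Cycles 2, 4, 6 and 8: 4 events, 0 consecutive pairs, 0 required reductions.
- If counts fall and recover before the next planned infusion, there is no hold, so the recurrence rule is not triggered.

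The documents give no rate of DLT-level cytopenia for this drug, so the number of patients affected cannot be estimated from them.

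**The case against.** **Hold, recover, reduce on recurrence is an established pattern here.** A non-anaphylactic Grade 3 infusion reaction may continue at the same dose. A first symptomatic ocular finding is held and re-treated with no required reduction. Section 5.1.2.2 also defers to Table 3 by design. This is fair, and it shows that same-dose re-treatment is not in itself an error. It does not explain why one hematologic event has a lower restart dose in escalation Cycle 1 and no default afterwards.

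**Other safeguards exist.** They do, and they narrow the point. Delays beyond 14 days for toxicity need Medical Monitor approval or the patient stops (5.1.2.1). Section 4.6.1 requires discontinuation for any condition judged to jeopardize safety. Section 4.5 allows dosing only with acceptable laboratory values, and Table 3's ANC and platelet limits for resuming equal the entry limits in Section 4.1.1. These control whether and when a patient is re-treated; none sets the dose.

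**The drug's own signal is mild.** Section 5.1.1.3 reports only mild decreases in lymphocytes, eosinophils and reticulocytes in monkeys. That lowers the expected frequency but does not settle it in a first-in-human study.

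**Readings that go too far.** A reader might infer that every hematologic DLT falls in the gap. Febrile neutropenia and thrombocytopenia with significant bleeding have clinical components that arguably come under Section 5.1.2.2, so the point is limited to isolated laboratory cytopenias. A reader might also infer that four events must occur before treatment stops: two holds at full dose, then two at the reduced dose. That counts Table 3 alone; one slow-recovering event, or a safety judgment, can end treatment.

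**Conclusion.** The gap is real and narrow. For a first isolated DLT-level laboratory cytopenia in Cycle 2 or later of escalation, or in any cycle of expansion, the protocol allows full-dose re-treatment after recovery and has no default reduction. In expansion the allowed dose is 1.33 to 2.0 times what Section 5.1.2.2 would give after other related Grade 3 or higher toxicity; one step down from 2.4 or 1.2 mg/kg in escalation corresponds to a factor of 2.0. These are upper limits on the difference, because an investigator may choose to reduce.

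The documents do not support saying that full-dose re-treatment is required or that reduction is barred: Section 5.1.2.1 permits it. Nor do they support calling Section 5.1.2.2 an absolute mandate, since it says both that the drug may restart at a reduced dose and that the dose should be reduced. Cohort monitoring is not at fault either: Section 3.1.2 still weighs the frequency of Grade 3–4 toxicity, and the stopping decision in Section 6.1.2 takes other safety events into account. The conclusion rests on reading Section 3.1.1.4's restart rule as confined to escalation Cycle 1, as its placement and wording indicate. It merits a short amendment and does not call the design into question.

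**What to change.** Add to the hematologic row of Table 3:

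> After a first hematologic event that meets a Section 3.1.1.1 criterion, in any cycle, resume at a reduced dose using the steps in Section 5.1.2.2 (next lowest tested level in escalation; about 25%–50% lower in expansion), unless the Medical Monitor approves otherwise; patients at the lowest tested level are to be discussed with the Medical Monitor. For Cycle 1 DLTs in escalation, Section 3.1.1.4 applies.

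Leave milder cytopenias as they are. The Medical Monitor exception is needed because a strict reduced-dose-only rule would leave a patient at 0.6 mg/kg with no way to resume.

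The cost is two sentences, with no new visits or tests. A few patients would receive a lower dose after an event from which they had recovered. Each would use one of the two reductions allowed by Section 5.1.2.1, which does not permit a later increase.
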